2.5. Preparation of the program

Since there is no standard training module on pain management in children, the training content was prepared by researchers based on a literature review (Büyükgönenç & Törüner, 2018; IASP, 2018; ChildKind International, 2020; WHO, 2012; WHO, 2020). The content was evaluated by 10 faculty members specializing in pediatric nursing and revised based on their feedback. Presentations were prepared and video lessons were created based on this content. In the study, the same training programs were prepared for the intervention and control groups. Weekly

topics and training duration were kept equal for both groups. Teaching methods and techniques were structured based on the "Flipped Classroom Model" for the intervention group and the "Self-Directed Learning Model" for the control group.

The training process lasted four weeks, with each week focusing on a different topic:

- 1. Week 1: Introduction to pain,
- 2. Week 2: Pathophysiology of pain and management challenges,
- 3. Week 3: Diagnosis and assessment,
- 4. Week 3: Pain control.

2.6. Application of the flipped learning approach in the intervention group

Students in the intervention group watched lecture videos on relevant topics one week before classroom activities. Students accessed the lecture videos through the https://www.e-pediatri.com platform, developed by researchers using the Tutor LMS system. Tutor LMS was chosen as an effective learning management system due to its user-friendly mobile-supported interface, flexible configuration options, and comprehensive monitoring and evaluation tools. Students logged into the platform with their username and password to access course materials anytime and anywhere and review the materials repeatedly.

Classroom activities were conducted once a week for four weeks, consisting of online sessions lasting approximately 20-25 minutes. These sessions were conducted using interactive techniques in line with the flipped learning approach via the Google Classroom infrastructure integrated into the https://www.e-pediatri.com platform. In the classroom sessions, various student-centered activities such as mini tests, case studies, article reviews, concept maps, and group discussions were implemented to ensure active student participation. These methods were used to help students understand the topics in terms of cause-and-effect relationships and to increase the retention of learning.

2.7. Application of the self-directed learning approach to the control group

The same educational videos were uploaded simultaneously to the university's Distance Education Center (UZEM) platform for the students in the control group. Students were allowed to watch the videos individually, and no online classroom interaction was conducted throughout the process. The learning process was supported by assignments given to students and online educational materials. The assignments completed by students were evaluated, and feedback was provided to them. The duration of the training was kept equal for both groups.

To minimize contamination risk, the intervention group's training was conducted through the e-pediatri.com platform, while the control group's training was conducted through the university's UZEM platform in sessions of equal duration.

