2.2.3. Motivation Questionnaire Regarding Teaching Materials

The Teaching Material Motivation Survey (ÖMMA) was developed by Keller and its validity and reliability were studied in Turkish by Kutu and Sözbilir (Keller, 2006; Kutu & Dir, Sözbilir, 2011). This scale, which aims to determine students' motivation levels toward instructional materials, consists of a total of 24 items on a 5-point Likert scale. The items in the attention-appropriateness dimension of the ÖMMA are 1, 2, 3, 4, 5, 6, 7, 8, 9, 10, and 11; while the items in the confidence-satisfaction dimension are 12, 13, 14, 15, 16, 17, 18, 19, 20, 21, 22, 23, and 24. Five items in the questionnaire (3, 12, 14, 16, 18) were reverse-coded. The minimum score in the questionnaire is 24, and the maximum score is 120. A high score on the survey indicates high motivation regarding the teaching material. The Cronbach's alpha coefficient is 0.83. In this study, the Cronbach's alpha value was found to be 0.789.

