3.3. Findings Related to Motivation Levels

Findings related to students' motivation levels are summarized in Table 3. There was no significant difference in motivation level scores between students in the intervention group and those in the control group in the pre-test (p > 0.05). However, when the results of the two-way mixed design ANOVA were examined, group effect (F=39.206, p < 0.001, η^2 =0.323), time effect (F=67.749, p<0.001, η^2 =0.452), and group*time interaction (F=70.240, p<0.001, η^2 =0.461) were found to be statistically significant. The significance of the group*time interaction indicates that the effect of the time factor on motivation levels is not the same for both groups (Table 3).

In the entrepreneurial group that received education with the flipped classroom model, a significant increase was observed in students' motivation scores. The average score, which was 83.61 ± 12.61 in the pre-test, increased to 120.66 ± 17.20 in the post-test and was recorded as 101.50 ± 12.26 in the retention test. The use of different letters (a, b, c) to denote the averages at different measurement times indicates statistically significant differences over time. In contrast, the motivation level scores of the control group, which received education using the self-learning model, remained quite close to each other at all time points, and no significant change was observed (pre-test: 86.76 ± 12.03 , post-test: 86.40 ± 11.91 , retention test: 85.61 ± 12.36). These findings indicate that the flipped classroom model is more effective than the self-directed learning model in enhancing students' motivation (Figure 2).

Table 3. Learning Motivation Scores of the Intervention and Control Groups

Motivation Survey Regarding Teaching	Intervention group (n=44) Mean (SD)	Control group (n=44) Mean (SD)	Statistic	Group	Time	Group*time interaction
Materials Pre-test	83.61 (12.61) ^a	86.76 (12.03) ^a	F	39,206	67,749	70,240
Post-test (4th week)	120.66 (17.20) ^b	86.40 (11.91) ^a	p	<0.001	<0.001	<0.001
Retention Test (3rd month)	101.50 (12.26)°	85.61 (12.36) ^a	η^2	0.323	0.452	0.461

a-c: Different letters indicate statistically significant groups within each column.

F: Two-way mixed design analysis of variance; η^2 , partial eta square; SD, standard deviation.

[figure not shown]

Figure 2. Mean Scores of Learning Motivation by Group and Time

4. Discussion

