In addition to these comprehensive cognitive contributions, the uniqueness of the study area is also noteworthy. The limited number of studies evaluating the effectiveness of the flipped classroom model in narrow and clinically critical areas such as pediatric pain management using a randomized controlled design increases the contribution of the findings to the literature.

The findings indicate that the flipped classroom approach is more effective than the traditional self-learning model in terms of increasing and maintaining knowledge levels in both the short and long term. This result shows that active classroom interaction and practical work carried out after the pre-learning process contribute positively to the retention of learning. Indeed, studies conducted by Sáiz-Manzanares et al. (2020) also emphasize that learning environments with high levels of active participation have a significant impact on knowledge retention (Sáiz-Manzanares et al., 2020).

However, some limitations of this model have also been noted in the literature. In particular, it has been pointed out that factors such as difficulty in accessing digital materials and insufficient assumption of individual learning responsibility may negatively affect student motivation (Busebai & John, 2021). However, in this study, maintaining a strong technical infrastructure and ensuring high accessibility of the digital platform used minimized such negative effects and supported the effectiveness of the learning process.

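### Teaching platform coincides completely with arm, so the trial estimates the effect of a delivered package and cannot assign that effect to the flipped classroom model alone

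*Combined protocol and SAP*

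**What the plan says.** Section 2.5 presents the training programme, weekly topics and duration as the same in both arms, with the teaching method as the difference. Sections 2.6 and 2.7 then describe two delivery systems.

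- **Intervention (2.6).** Videos were on e-pediatri.com, "developed by researchers using the Tutor LMS system", a system selected for its "user-friendly mobile-supported interface, flexible configuration options, and comprehensive monitoring and evaluation tools". Weekly live sessions ran through Google Classroom integrated into that site.
- **Control (2.7).** "The same educational videos were uploaded simultaneously to the university's Distance Education Center (UZEM) platform". There was no live online interaction; students received assignments with feedback.
- **Reason for two platforms (2.7).** The arrangement is given as protection against contamination: "the intervention group's training was conducted through the e-pediatri.com platform, while the control group's training was conducted through the university's UZEM platform". Section 7 repeats this as a strength. The limitations do not mention it.
- **Role of the platform (4.1).** After noting that difficulty with digital access may lower motivation, the discussion says that "ensuring high accessibility of the digital platform used minimized such negative effects and supported the effectiveness of the learning process".
- **Attribution (3.3).** "These findings indicate that the flipped classroom model is more effective than the self-directed learning model in enhancing students' motivation". Section 3.2 makes the same attribution for knowledge. The abstract's conclusion and section 6 credit the model, and section 5 builds its curriculum advice on it.
- **Motivation outcome (2.2.3).** "A high score on the survey indicates high motivation regarding the teaching material". Two dimensions and their item numbers are given, but no item wording.

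**The concern.** Hypotheses 1 and 2 are about the teaching model. The introduction defines that model as online theory outside class with class time kept for application, and ties it to no particular platform. The arms differed in the intended way (live interactive sessions or none) and also in the system on which students met the material. When two differences always occur together, randomisation protects the comparison of the two bundles but not the attribution to one component.

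At stake is what the trial may conclude. A school that adopted live flipped sessions on its existing learning system would be relying on a contrast that this trial did not make. The same limit applies to the primary outcome (knowledge) and the secondary outcome (motivation).

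**Working it through.** **1. Can platform and model be separated?** For a student's score, write

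E(Y) = b0 + b1 × arm + b2 × platform,

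with arm = 1 for flipped and platform = 1 for e-pediatri.com. By sections 2.6 and 2.7, platform = arm for every student. The difference between arms is therefore b1 + b2, and no contrast in the data isolates b1. A design matrix for 42 + 42 students with columns for intercept, arm and platform has rank 2, not 3. Adding time and group × time terms changes nothing, because the two variables are identical at every visit. The analysis in section 2.10 has no platform term and could not have had one.

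**2. What the sum b1 + b2 amounts to.** Tables 2 and 3 are headed n = 44 per arm, while the abstract and Table 1 give 42. The printed partial eta squared values settle which number was analysed. For each effect, η² = F / (F + N − 2).

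| Effect | F | η² with N = 84 | η² with N = 88 | Printed |
|---|---|---|---|---|
| Knowledge, group | 16.789 | 0.170 | 0.163 | 0.170 |
| Knowledge, group × time | 27.834 | 0.253 | 0.245 | 0.253 |
| Motivation, group | 39.206 | 0.323 | 0.313 | 0.323 |
| Motivation, group × time | 70.240 | 0.461 | 0.450 | 0.461 |

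The printed values match 84 students, so n = 42 per arm is used below. The pooled SD is √[(s₁² + s₂²)/2] and the standard error is pooled SD × √(2/42), with t on 82 degrees of freedom. For post-test motivation: 120.66 − 86.40 = 34.26; pooled SD = √[(17.20² + 11.91²)/2] = 14.79.

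| Outcome and time | Difference | 95% CI |
|---|---|---|
| Motivation, pre-test | −3.15 | −8.50 to 2.20 |
| Motivation, post-test | 34.26 | 27.84 to 40.68 |
| Motivation, retention | 15.89 | 10.55 to 21.23 |
| Knowledge, post-test | 27.83 | 19.29 to 36.37 |
| Knowledge, retention | 15.10 | 6.41 to 23.79 |

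Each row is a package contrast. The data place no bound on the share due to the platform.

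**3. A caution on one row.** Section 2.2.3 gives a scale maximum of 120. A mean of 120.66 exceeds it by 0.66, which is impossible if the range and scoring are as stated. The 34.26 is therefore shown as printed and is not evidence of size until this is reconciled.

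**4. Do the documents supply outside information on b2?** No. UZEM's usability is never described, no viewing or usage data are reported for either arm, and the questionnaire items are not printed. The statement in section 4.1 treats the platform as a contributor, but it does not compare the two systems.

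**The case against.** The strongest defence has four parts.

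- **Online delivery belongs to the flipped model.** This stands in part. The introduction includes out-of-class online content in the definition, and sections 4.2 and 5 also credit content design, interaction and remote access. The documents are therefore not uniform in crediting the model alone, and the fault is largely one of imprecise labelling. But the control arm also learned online from the same videos, and the definition requires no particular platform, so the change of platform is not part of the model.
- **Separate sites protect against contamination.** This stands as a reason. The students came from one course cohort, and separation was a real aim. It explains the choice without removing the aliasing. Nothing in the documents shows that separate courses on one platform would protect as well, so that is not claimed here.
- **No platform effect has been shown.** This is correct. A reader might infer that UZEM was harder to use, or that control students watched fewer videos. The stated reasons for choosing Tutor LMS are not a comparison with UZEM, and internet access with a computer or smartphone was an inclusion criterion for everyone.
- **The motivation questionnaire may not touch the platform.** This is also correct. Because it concerns teaching material, a reader might infer that it rates access or interface. Without the items, that cannot be established.

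**Conclusion.** The point holds as a limit on attribution. Platform is fully aliased with arm, so both outcomes are tested only for the delivered package. This rests on one reading of sections 2.6 and 2.7: that all students used the platform assigned to their arm, which is how both sections describe it.

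It does not follow that the flipped model had no effect, or that the observed gains come from the platform. The live sessions were a substantial and intended difference, and the randomised comparison of packages remains a legitimate one. The size and direction of any platform contribution are unknown and cannot be recovered by reanalysis. No reported statistic changes because of this point; what changes is the claim that the statistics can support.

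**What to change.** **For the trial as run** (completed July 2022):

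- Reword the conclusions in the abstract and in sections 3.2, 3.3, 5 and 6 as a package effect, for example: *flipped sessions delivered on a purpose-built platform, compared with the same videos plus assignments with feedback on the university platform*.
- Leave Hypotheses 1 and 2 as stated, and say in the report that they are tested only at package level.
- In section 7, move the two-platform arrangement from strengths to limitations. It may still be described there as a contamination measure. Do not add any statement that UZEM was less usable.
- Reconcile the post-test motivation mean of 120.66 with the scale maximum of 120 before quoting the 34.26-point difference.

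The cost of the rewording is a few sentences and a narrower claim; it needs no new data or analysis. The last item needs a check of the motivation scoring.

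**For a repeat trial:** consider hosting both arms as separate access-controlled courses on one platform, with the live-session module open only to the intervention arm. Section 2.6 already describes individual usernames and passwords. The cost is setting up a second course and a possible loss of separation between arms, to be weighed against the cleaner contrast.

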2.8. Data collection

In the study, pre-tests were administered before the training; post-tests were administered one month after the completion of the training modules, and retention tests were administered three months after the completion of the training.

All data collection for the intervention and control groups was conducted online. The questionnaires and scales used were distributed to participants via Google Forms, and students were asked to fill out the forms on their own devices. No changes were made to the primary (pediatric pain management knowledge level) and secondary (learning motivation) outcome measures defined at the beginning of the study during the data collection process.

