4.2. The Effect of the Flipped Classroom Model on Learning Motivation

Statistically significant increases in the motivation levels of students who received education through the flipped classroom model were recorded in both the short and long term. In contrast, no significant change in motivation scores was observed in the control group where the self-directed learning model was applied. These findings indicate that the flipped classroom approach is effective in increasing students' interest in the material, encouraging active participation in class, and supporting intrinsic motivation.

In the literature, the positive effect of the flipped classroom model on learning motivation is supported by various studies. According to systematic reviews and meta-analyses conducted by Betihavas et al. (2016) and Liu et al. (2018), flipped classroom models have been found to have significant positive effects on learning motivation, autonomy, and self-efficacy (). In particular,

applications supported by case-based and problem-focused learning methods are noted to more effectively engage students in the learning process and enhance motivation (Merrou et al., 2023).

However, studies also highlight that this positive effect on motivation is not always sustainable. Some findings have revealed that the flipped classroom model creates high motivation among students in the initial stage, but motivation decreases over time when digital content is presented in an uninteractive, repetitive, or inadequate manner (Lo & Emp; Hew, 2019; Betihavas et al., 2016). This situation demonstrates that not only the structure of the learning model but also the quality of the content presented and the level of interaction are decisive factors in the sustainability of motivation.

Among the key factors that enable motivation to be sustained in the long term are the timeliness of content, diversity of applications, active participation of students in the learning process, and quality of interaction with instructors (Chen et al., 2014; Martin et al., 2020). Indeed, in this study, the fact that motivation scores remained high even in the retention test compared to the initial level suggests that the pedagogical quality of the content design and the intensity of interaction in the learning environment played a supportive role in motivation.

5. Nursing Education Implications

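### The motivation pre-test came before students had used the material that the questionnaire rates, so within-arm change in motivation cannot be interpreted; the between-arm comparison stands

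*Combined protocol and SAP*

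**What the plan says.** Section 2.2.3 describes an instrument that "aims to determine students' motivation levels toward instructional materials" and adds: "A high score on the survey indicates high motivation regarding the teaching material". On its range it says: "The minimum score in the questionnaire is 24, and the maximum score is 120".

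Section 2.5 gives the origin of the material: "Since there is no standard training module on pain management in children, the training content was prepared by researchers". Section 2.6 puts the videos on the flipped arm's platform as part of the training. For the control arm, Section 2.7 says: "The same educational videos were uploaded simultaneously to the university's Distance Education Center (UZEM) platform". Section 2.4 limits entry to students taking the course for the first time and excludes those with earlier training in pediatric pain management.

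On timing, Section 2.8 says that "pre-tests were administered before the training". The same section refers to the "secondary (learning motivation) outcome measures defined at the beginning of the study" and states that they did not change.

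Section 2.10 applies a two-group mixed ANOVA over time, and Table 3 shows three time levels for motivation, the first being the pre-test. From these, Section 3.3 reports a significant rise in the flipped arm and no significant change in controls. Section 4.2 draws support from "the fact that motivation scores remained high even in the retention test compared to the initial level". The abstract describes the gains as sustained. Hypothesis 2 itself is a statement about the two groups, not about change from the start.

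**The concern.** A score that rates a particular set of materials needs those materials to have been seen. At pre-test neither arm had opened the videos or joined a session, and the entry criteria make it unlikely that students had met other training on the same topic. The documents name no other object for the pre-test and do not say that the items were reworded. The answers can refer only to expectations or to some other, unnamed material. The two later tests rate the study material.

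The three scores are nevertheless analysed and described as repeated measurements of one quantity. At stake are the motivation time effect, the letters that mark differences between times within an arm, and every sentence that reads a motivation score against its starting level. The sustainability claim is the most exposed, because it depends on the pre-test as the reference.

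**Working it through.** **Inputs.** Motivation means (SD) from Section 3.3 and Table 3:

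| | Pre-test | Post-test | 3 months |
|---|---|---|---|
| Flipped | 83.61 (12.61) | 120.66 (17.20) | 101.50 (12.26) |
| Control | 86.76 (12.03) | 86.40 (11.91) | 85.61 (12.36) |
| Flipped − control | −3.15 | 34.26 | 15.89 |

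The group size is 42 per arm (abstract, Table 1). Table 3 is headed 44 per arm; the next step shows which number the analysis used.

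**1. Reproducing the reported figures.** Partial η² = F/(F + N − 2). With N = 84:
- group: 39.206/(39.206 + 82) = 0.3235 (reported 0.323)
- time: 67.749/(67.749 + 82) = 0.4524 (reported 0.452)
- interaction: 70.240/(70.240 + 82) = 0.4614 (reported 0.461)

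With N = 88 the values would be 0.313, 0.441 and 0.450, so the analysis used 84 students. As a second check, the interaction F can be rebuilt from all six cell means. The error mean square implied by the time F is 7085.35/67.749 = 104.58, and the interaction mean square is 7348.20, so F = 7348.20/104.58 = 70.26 (reported 70.240). This agrees with a model in which the pre-test is one of three time levels.

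**2. What depends on the pre-test.**
- Flipped arm: 120.66 − 83.61 = +37.05 and 101.50 − 83.61 = +17.89.
- Control arm: 86.40 − 86.76 = −0.36 and 85.61 − 86.76 = −1.15.

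These four differences lie behind the statements of a rise, of no change and of a level still above the start. Each subtracts a score with no stated object from a score that rates the study material.

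**3. Change over the two times that share an object.** From post-test to 3 months the flipped arm goes from 120.66 to 101.50, a fall of 19.16. Controls go from 86.40 to 85.61, a fall of 0.79. The gap between arms goes from 34.26 to 15.89, a little under half.

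**4. The between-arm comparison without the pre-test.** Welch comparison, SE = √(SD₁²/42 + SD₂²/42):
- Post-test: SE = √((17.20² + 11.91²)/42) = 3.23; t = 34.26/3.23 = 10.6; 95% CI 27.8 to 40.7.
- 3 months: SE = √((12.26² + 12.36²)/42) = 2.69; t = 15.89/2.69 = 5.92 (from the unrounded SE); 95% CI 10.5 to 21.2.

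Both p-values are below 0.001, so the result is the same at the 0.05 of Section 2.3 and at the 0.005 of Section 2.10.

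**5. The group main effect.**
- Over three times: (−3.15 + 34.26 + 15.89)/3 = 47.00/3 = 15.67.
- Over the two post-exposure times: (34.26 + 15.89)/2 = 25.08.

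**6. The pre-test gap.** −3.15, SE = √((12.61² + 12.03²)/42) = 2.69, t = −1.17, p = 0.24.

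**The case against.** The strongest reply is that the arms were randomised and took the same pre-test at the same stage. Whatever students rated then, its expected value is the same in both arms. The difference between arms in change therefore estimates the same effect as the difference after exposure; an ill-defined pre-test adds noise, not bias. This stands. A reader might infer that the group × time interaction is invalid, or that only a post-exposure comparison can address Hypothesis 2. The documents do not support either: the interaction still signals a difference between arms, though not a change in motivation toward this material.

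A reader might also infer that the pre-test inflates the effect. The contrasts in change are 37.05 + 0.36 = 37.41 and 17.89 + 1.15 = 19.04, larger than 34.26 and 15.89 by 3.15 points (9% and 20%). But that excess is simply the pre-test gap, which is compatible with chance. A perfectly well-defined baseline with the same gap would give the same percentages. The planned group main effect moves the other way and is made smaller by the pre-test.

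Finally, the item wording and pre-test instructions are not in the documents, and students may have been asked about existing course material. That is possible, and it is why the first request is to state what was rated. It does not rescue the within-arm readings: the pre-test would then have an object, but a different one from the later tests.

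**Conclusion.** The point holds for the time effect, the within-arm letters and the wording in the abstract and Sections 3.3 and 4.2 that reads motivation against its starting level. None of these can be taken as change in motivation toward the study material.

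The evidence for Hypothesis 2 is not overturned on this ground. At the printed means the arms differ by 34.26 points at post-test and 15.89 at 3 months, and neither figure needs a baseline. The group main effect is a poor summary of this, at 15.67 against 25.08. That dilution would occur with any pre-intervention time level, however well defined.

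The conclusion rests on three assumptions:
- No unpublished instruction gave the pre-test the same object as the later tests. None is apparent, since the material was new.
- Pre-test answers were not influenced by knowledge of the assigned arm. This matters for the interaction and for use as a covariate; the text does not say whether allocation was known at that time.
- The printed means are correct. The flipped post-test mean of 120.66 cannot be, if the maximum is 120, so the 34.26 and every figure built on it are provisional. The 3-month difference does not use that mean.

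The issue concerns a secondary outcome. The knowledge scale does not rate the study material and is unaffected.

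**What to change.** 1. Resolve the post-test mean of 120.66 against the stated maximum of 120 before any motivation re-analysis.
2. State in Sections 2.2.3 and 2.8 what students were asked to rate at the pre-test and whether the items were reworded.
3. In Section 2.10, test Hypothesis 2 on motivation as flipped minus control at post-test and at 3 months. Remove the pre-test as a time level; use it only as a covariate, labelled for what it measured.
4. Remove the within-arm change statements and the claims of a level sustained above the start for motivation from the abstract and Sections 3.3 and 4.2. Any statement on persistence should rest on the between-arm difference at the two post-exposure times.
5. Describe the outcome throughout as motivation toward the teaching material, not as general or intrinsic learning motivation (Sections 4.2 and 5).

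The cost is a change of wording and one re-run on data already held, once the out-of-range mean is explained. The claim of change over time is lost for this secondary outcome; the between-arm result is kept.
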